8.2. POPULATION PHARMACOKINETIC (POPPK) ANALYSES

PK samples will be analysed periodically throughout the study duration to enable development of a preliminary population PK model. If appropriate, a population PK analysis may also be conducted on the final data. In addition the oxytocin plasma concentration-time data may be merged with historical data and analysed as part of a population PK meta-analysis. The timeline for these analyses will be independent of the analysis described in this RAP. To support this analysis a NONMEM-specific data file will be generated, the specifications of which are provided in POP PK RAP appendix.

8.3. Exploratory Pharmacokinetic Analyses: Group 2

8.3.1. Endpoint / Variables : Group 2

- Pre-dose plasma concentrations of oxytocin.
- For IH formulation: - Cp10, Cp20, Cp30, Cmax, Tmax, AUC(0-3h), Area under the concentration time curve from time zero to infinity (AUC[0-∞]) and t1/2, will be compared as data permit.
- For IV formulation: - Cmax, AUC(0-inf), AUC(0-3h), t1/2, CL and Volume of distribution (VOD) will be compared as data permit.

8.3.2. Summary Measure: Group 2

Descriptive Statistics will be produced for Pre-dose plasma concentrations of oxytocin. Pharmacokinetic data will be presented in graphical and/or tabular form and will be summarized descriptively by cohort

As the number of subjects required to statistically compare IV Bolus Oxytocin and IV Infusion Oxytocin between Cohort A and Cohort B is not sufficient, only summary statistics will be produced for IV Bolus Oxytocin and IV Infusion oxytocin. The Inhaled oxytocin will be statistically compared between Cohort A and Cohort B as described in Section 8.3.4

8.3.3. Population of Interest: Group 2

The exploratory pharmacokinetic analyses will be based on the Pharmacokinetic population, unless otherwise specified

CONFIDENTIAL

205920

8.3.4. Statistical Analyses / Methods: Group 2

Details of the planned displays are provided in [Appendix 12: List of Data Displays](#) and will be based on GSK Data Standards and statistical principles.

The following pharmacokinetic statistical analyses will only be performed, if sufficient data is available (i.e. if subjects have well defined plasma profiles). Pharmacokinetic analysis will be the responsibility of the Clinical Pharmacology Modelling and Simulation Department, (CPMS) and Statistical analyses of the pharmacokinetic parameter data will be the responsibility of Clinical Statistics (CS).

To compare the IH pharmacokinetics of oxytocin between Cohort A (subjects on combined oral contraceptive) and Cohort B (subjects using a non-hormonal form of contraception), point estimates and corresponding two-sided 90% confidence intervals will be computed for Cp10, Cp20, Cp30, Cmax, Tmax, AUC(0-3h), Area under the concentration-time curve from time zero to infinity (AUC[0-∞]) and t1/2.

Data will be loge-transformed prior to analysis using a mixed effect model with a fixed effect term for cohort and a random effect term for subject, with the exception of T1/2 and Tmax which will be analysed non-parametrically using Mann Whitney test.

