2.4. Statistical Hypotheses / Statistical Analyses

No formal hypotheses will be tested.

For IH and IM oxytocin, summary statistics will be produced separately for IH Oxytocin and IM Oxytocin. Due to sparse PK concentrations, it is not possible to include a formal statistical analysis to compare IH and IM Oxytocin. PK parameters will be derived as data permit. Individual plots, listings and summary tables will be produced for available PK concentration data. Only listings and summary tables will be produced for PK Parameter data.

3. PLANNED ANALYSES: GROUP 1

3.1. Interim Analyses: Group 1

No formal Interim Analysis are planned, however, PK samples will be analysed and preliminary PK parameters derived following completion of approximately 5 women on each treatment group: 400 mcg IH and 10 I.U. IM to women in TSL (Group 1) and 400 mcg IH to non-pregnant women on the combined oral contraceptive (Group 2 Cohort A), in order to assess if dose escalation is required.

Due to sparse PK concentration-time data available following administration of IH and IM oxytocin to women in TSL, only concentration time plots were presented at the interim analysis. The Study has been terminated early due the unanticipated inability to be able to quantify plasma oxytocin using a selective and sensitive (LLQ 2pg/mL) analytical assay due to low oxytocin concentrations (<2pg/mL) in the majority of samples collected from women in Third Stage Labour (TSL), following either IM or IH administration. Therefore, the Primary objective of the study to characterise the PK of single doses of IH and IM oxytocin in women in TSL, cannot be met, and the study is being terminated

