
 To characterize the pharmacokinetics 	
 Plasma concentration time profile for IH oxytocin and 5

CONFIDENTIAL

205920

Objectives	Endpoints
of single doses of IH oxytocin and 5 I.U. IV oxytocin.	I.U. IV oxytocin. 
 PK parameters: Cmax, Cp10, Cp20, Cp30, tmax, AUC, Plasma clearance (CL), volume of distribution and t1/2 will be calculated as data permit.
Exploratory Objectives	Exploratory Endpoints

 To evaluate endogenous plasma oxytocin concentrations in non-pregnant females in the presence and absence of the combined oral contraceptive. 	
 Pre-dose plasma concentrations of oxytocin.

 To compare the IH pharmacokinetics of oxytocin between Cohort A (subjects on combined oral contraceptive) and Cohort B (subjects using a non-hormonal form of contraception). 	
 Cp10, Cp20, Cp30, Cmax, AUC(0-3h), Area under the concentration time curve from time zero to infinity (AUC[0-∞]) and t1/2, will be compared as data permit.

 To compare the IV pharmacokinetics of oxytocin between Cohort A and Cohort B. 	
 Cmax, AUC, t1/2, CL and Volume of distribution (VOD) will be compared as data permit.

Groups 1 and 2 – Women in TSL and Non-pregnant, non-lactating females of child bearing potential

Objectives	Endpoints
Primary Objectives	Primary Endpoints

 To compare pharmacokinetics of IH oxytocin between Group 1 and Group 2 	
 Cp10, Cp20, Cp30, AUC(0-3h) Cmax, AUC(0-3h) AUC(0-∞), and t1/2 will be compared as data permit.

CONFIDENTIAL

205920

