7.3. Other Safety Analyses

The analyses of non-laboratory safety test results including ECGs and vital signs will be based on GSK Core Data Standards, unless otherwise specified. The details of the planned displays are presented in [Appendix 12: List of Data Displays](#).

CONFIDENTIAL

205920

8. PHARMACOKINETIC ANALYSES : GROUP 2

8.1. Primary Pharmacokinetic Analyses : Group 2

8.1.1. Endpoint / Variables : Group 2

- Plasma concentration time profile for IH oxytocin and 5 I.U. IV oxytocin.
- PK parameters: C_{max}, C_{p10}, C_{p20}, C_{p30}, t_{max}, AUC(including AUC(0-t), AUC(0-inf) and AUC(0-3h)), Plasma clearance (CL), volume of distribution and t_{1/2} will be calculated as data permit

8.1.1.1. Drug Concentration Measures : Group 2

Refer to [Appendix 5: Data Display Standards & Handling Conventions \(Section 10.5.3. Reporting Standards for Pharmacokinetic\)](#)

8.1.1.2. Derived Pharmacokinetic Parameters: Group 2

Pharmacokinetic parameters will be calculated by standard non-compartmental analysis according to current working practices and GSK procedures using the currently supported version of WinNonlin. All calculations of non-compartmental parameters will be based on actual sampling times. Pharmacokinetic parameters listed will be determined from the plasma concentration-time data, as data permits.

Treatment	Parameter	Parameter Description
IH/IV	C _{max}	Maximum observed concentration, determined directly from the concentration-time data.
IH/IV	Pre - dose	Quantified concentration in PK sample collected at predose, determined directly from the concentration-time data.
IH	C _{p10}	Quantified concentration in PK sample collected at 10 minutes (nominal time) post-dose, determined directly from the concentration-time data.
IH	C _{p20}	Quantified concentration in PK sample collected at 20 minutes (nominal time) post-dose, determined directly from the concentration-time data.
IH	C _{p30}	Quantified concentration in PK sample collected at 30 minutes (nominal time) post-dose, determined directly from the concentration-time data.
IH/IV	t _{max}	Time to reach C _{max} , determined directly from the concentration-time data.
IH/IV	AUC(0-t)	Area under the concentration-time curve from time zero to the time of the last quantifiable concentration (C(t)) will be calculated using the linear trapezoidal rule for each incremental trapezoid and the log trapezoidal rule for each decremental trapezoid.

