10.5.2. Reporting Standards

General	

 The current GSK Integrated Data Standards Library (IDSL) will be applied for reporting, unless otherwise stated (IDSL Standards Location: https://spope.gsk.com/sites/IDSLLibrary/SitePages/Home.aspx): 
 4.03 to 4.23: General Principles 5.01 to 5.08: Principles Related to Data Listings 6.01 to 6.11: Principles Related to Summary Tables 7.01 to 7.13: Principles Related to Graphics 	
Formats	

 All data will be reported according to the actual treatment the subject received unless otherwise stated. GSK IDSL Statistical Principles (5.03 & 6.06.3) for decimal places (DP's) will be adopted for reporting of data based on the raw data collected, unless otherwise stated. Numeric data will be reported at the precision collected on the eCRF. The reported precision from non eCRF sources will follow the IDSL statistical principles but may be adjusted to a clinically interpretable number of DP's. 	
Planned and Actual Time	

 Reporting for tables, figures and formal statistical analyses: 
 Planned time relative to dosing will be used in figures, summaries, statistical analyses and calculation of any derived parameters, unless otherwise stated. The impact of any major deviation from the planned assessment times and/or scheduled visit days on the analyses and interpretation of the results will be assessed as appropriate. Reporting for Data Listings: 
 Planned and actual time relative to study drug dosing will be shown in listings (Refer to IDSL Statistical Principle 5.05.1). Unscheduled or unplanned readings will be presented within the subject's listings. 	
Unscheduled Visits	

 Unscheduled visits will not be included in summary tables and/or figures. All unscheduled visits will be included in listings. 	

CONFIDENTIAL

205920

Descriptive Summary Statistics		
Continuous Data	Refer to IDSL Statistical Principle 6.06.1	
Categorical Data	N, n, frequency, %	
Reporting of Pharmacokinetic Concentration Data		
Descriptive Summary Statistics	Refer to IDSL Statistical Principle 6.06.1 Assign zero to NQ values (Refer to GUI_51487 for further details)	
Reporting of Pharmacokinetic Parameters		

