Descriptive Summary Statistics. (Loge Transformed)	N, n, geometric mean, 90% CI of geometric mean, standard deviation (SD) of logged data and between geometric coefficient of variation (CVb (%)) will be reported. $CVb (\%) = \sqrt{(\exp(SD^2) - 1) * 100}$ [NOTE: SD = SD of loge transformed data] Following steps can be used to calculate 90% CI for PK parameters: Standard Error = [(Geometric Stdev-1)/Sqrt(N)], Margin of Error = [Standard Error * 1.645], and CI = [Geometric Mean \pm Margin of Error]	
Parameters Not Being Loge Transformed	Tmax, and t1/2	
Summary Tables	The following PK parameters will not be summarised: tlast, Lambda_z, Lambda_z_lower, Lambda_z_upper, #pts and r-squared . The following PK parameters will not be log-transformed: Tmax, t1/2 All other parameters will be summarised as log-transformed and non-log-transformed data as described in Section 8.1.2.	
Listings	Include PK Parameters Cmax, Clast, tmax, tlast, AUC(0-3h), AUC(0-t), AUC (0- ∞), Cp(10), Cp(20), Cp(30) , t1/2, Clearance (IV only), Volume of distribution (IV only), F (Inhaled Bioavailability) Lambda_z, Lambda_z_lower, Lambda_z_upper, #pts and r-squared as data permit	
Reporting of Partial Dose / No treatment		
If in a situation where a subject has received partial dose or a subject has received no treatment in a particular period, then they will be handled as given below:		
	Enrolled, Screened Population	Safety, PK Population
Listings, individual PK figures, Study Population tables without period treatment information	Include	Include
Summary PK figures, Safety and PK tables with treatment information	Include	Exclude
Graphical Displays		
Refer to IDSL Statistical Principals 7.01 to 7.13.		

CONFIDENTIAL

205920

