10.5.3. Reporting Standards for Pharmacokinetic

Pharmacokinetic Concentration Data	
PC Windows Non-Linear (WNL) File	PC WNL file (CSV format) for the non compartmental analysis by Clinical Pharmacology Modelling and Simulation function will be created according to IDSL Standards. Note: Concentration values will be imputed as per GUI_51487
Descriptive Summary Statistics, Graphical Displays and Listings	Refer to IDSL PK Display Standards. Refer to IDSL Statistical Principle 6.06.1. Note: Concentration values will be imputed as per GUI_51487 for descriptive summary statistics/analysis and summarized graphical displays only.
NONMEM/Pop PK File	Pop-PK file (CSV format) for the POP-PK analysis by Clinical Pharmacology Modelling and Simulation function will be created according to the data specification detailed in Section 9.1 Data Specification of the Pop-PK RAP (RAP-IVF116828-201558-205920-PopPK, located in Cabinets/Study File/GR121619/_Project/Meta Analysis/ RAP-IVF116828-201558-205920-PopPK)
Pharmacokinetic Parameter Derivation	
PK Parameter to be Derived by Programmer	The following PK parameters will be derived by the Programmer: Cp10, Cp20 and Cp30 and pre-dose
Pharmacokinetic Parameter Data	
Is NQ impacted PK Parameters Rule Being Followed	Yes, refer to Standards for Handling NQ Impacted PK Parameters
Descriptive Summary Statistics, Graphical Displays and Listings	Refer to IDSL PK Display Standards. Refer to Standards for the Transfer and Reporting of PK Data using HARP

CONFIDENTIAL

205920

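### Group 2's endogenous-oxytocin objective is summarised under NQ rules meant for administered drug, so its figures may largely reflect the assay limit if pre-dose levels lie near or below the LLQ

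*SAP*

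**What the plan says.** The point concerns the Group 2 RAP, with two facts taken from the Group 1 RAP.

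- **Objective (Group 2 RAP, 2.2, exploratory).** "To evaluate endogenous plasma oxytocin concentrations in non-pregnant females in the presence and absence of the combined oral contraceptive". The endpoint is the pre-dose plasma concentration.
- **Planned analysis (8.3.2).** "Descriptive Statistics will be produced for Pre-dose plasma concentrations of oxytocin". No model or test is planned for it; the mixed model and the Mann-Whitney test in 8.3.4 cover other parameters.
- **Concentration summaries (10.5.2).** "Assign zero to NQ values (Refer to GUI_51487 for further details".
- **Pre-dose as a derived parameter (8.1.1.2).** "Quantified concentration in PK sample collected at predose, determined directly from the concentration-time data". Section 10.5.3 adds: "The following PK parameters will be derived by the Programmer: Cp10, Cp20 and Cp30 and pre-dose".
- **Log summaries (10.5.2).** Pre-dose is neither among the parameters left unsummarised nor among those kept off the log scale, so it falls under "All other parameters will be summarised as log-transformed and non-log-transformed data as described in Section 8.1.2". That means a geometric mean, its 90% CI and %CVb.
- **NQ-affected parameters (10.5.3).** "Yes, refer to Standards for Handling NQ Impacted PK Parameters". That standard is not reproduced.
- **Sampling (10.2.1.2 and 10.6.1).** Each session has three pre-dose samples, about 1 hour, 30 minutes and 15 minutes before dosing. Multiple measurements at one analysis time point are averaged.
- **Group 1 RAP, 3.1.** The assay LLQ is 2 pg/mL, and quantification failed "due to low oxytocin concentrations (<2pg/mL) in the majority of samples collected from women in Third Stage Labour (TSL), following either IM or IH administration".
- **Group 1 RAP, 8.1.2 and Table 2.8.** Group 1 receives a frequency table of women with no, one, or two or more measurable concentrations. No display title in the Group 2 list corresponds to it.

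**The concern.** For an administered drug, a pre-dose zero usually states what is known: the drug has not been given. Here the substance is a hormone the body makes, and its undosed level is the endpoint. A zero then asserts absence where the assay shows only that the level is below its limit.

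Three consequences follow. The arithmetic mean is pulled down, and the median prints as 0 once more than half of the values are NQ. The log summary cannot use a zero, and this RAP does not say what happens to such values. If the three pre-dose samples are treated as one time point, the averaging rule mixes zeros with measured values.

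This is the plan's only look at whether the contraceptive is associated with a different natural oxytocin level. If many samples are NQ, a reader could not separate a cohort difference from a difference in how often the assay read anything.

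**Working it through.** The plan gives no NQ share or expected endogenous level, so there is no figure to reproduce. The check asks how far the zero rule moves the mean over a range of true levels.

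**Inputs from the documents**
- NQ set to zero: Group 2 RAP 10.5.2.
- LLQ L = 2 pg/mL: Group 1 RAP 3.1 only. The Group 1 mock shell PK_T1 gives half the LLQ as 5 pg/mL, which implies 2 × 5 = 10. The Group 2 RAP states no LLQ.

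**Assumptions, not in the documents**
- One lognormal value per woman, with true geometric mean (GM) m of 1, 2, 4 or 8 pg/mL and between-subject CV of 50% or 100%.
- Group 2 uses the same assay as Group 1.

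**Formulas**
- σ = √ln(1 + CV²), so 0.472 at CV 50% and 0.833 at CV 100%.
- z = ln(L/m)/σ, and NQ share = Φ(z).
- True mean = m·exp(σ²/2).
- Zero-substituted mean ÷ true mean = Φ(σ − z).
- GM of quantified values only = m·exp{σ·φ(z)/[1 − Φ(z)]}.

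**Worked case, m = 1, CV 100%.** z = 0.693/0.833 = 0.833, so NQ = Φ(0.833) = 79.7%. The true mean is 1.41. The ratio is Φ(0.833 − 0.833) = 0.50, so the zero-substituted mean is 0.71, or 50% low. The GM of quantified values would be 3.19.

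**Worked case, m = 1, CV 50%.** z = 0.693/0.472 = 1.467, so NQ = 92.9%. The ratio is Φ(0.472 − 1.467) = 0.16, so the mean is 84% low.

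| True GM (pg/mL) | NQ | Zero-substituted mean | Median with zeros | GM if NQ were dropped |
|---|---|---|---|---|
| 1 | 80-93% | 50-84% low | 0 | 147-219% high |
| 2 | about 50% | 20-32% low | 0 or about 2 | 46-94% high |
| 4 | 7-20% | 3-5% low | about 4 | 7-34% high |
| 8 | 0.2-5% | 0-1% low | about 8 | 0-9% high |

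The last column applies only if the unseen standard drops NQ values. The results depend on m/L alone, so with an LLQ of 10 the same rows hold at true GMs of 5, 10, 20 and 40 pg/mL.

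**Cohort contrast, true ratio 2.** For GMs of 1 and 2, the ratio of zero-substituted means is 3.2-8.5. For GMs of 4 and 8 it is 2.05-2.08. If NQ values were dropped, the GM ratio would be about 1.2 in the first case and 1.62-1.87 in the second.

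**Averaging three samples.** With readings NQ, NQ and 2.4 pg/mL, the zero rule followed by averaging gives (0 + 0 + 2.4)/3 = 0.8. That is below the LLQ and was not measured in any sample. The table above does not include this step.

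**The case against.** The strongest reply is that the documents do not show Group 2 to be affected. The LLQ and the NQ majority come from the Group 1 RAP and concern women in third stage labour, where the failure is called unanticipated. Group 2 was to be reported before Group 1 was complete, and Group 1's Table 1 calls its inhaled data sparse by comparison with Group 2. That remark concerns the comparison of inhaled PK and says nothing about endogenous levels. Even so, it argues against carrying Group 1's experience across. This stands: the size of the problem is conditional, and at several times the LLQ the zero rule does almost no harm.

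A reader might also infer that NQ values are left out of the log summaries, so that each cohort's GM must be at least 2 pg/mL. The definition of Pre-dose as a quantified value suggests this, but section 10.5.3 defers to a standard that may impute instead. The Group 1 mock shell does impute Cmax and AUC. The documents therefore do not support that inference as a fact.

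Nor is it certain that no Group 2 output counts NQ values. No display title does, but the contents of the standard shells are not shown, n is planned, and Listing 26 gives the individual concentrations.

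Finally, the objective is exploratory and descriptive, and no primary result depends on it. That limits the weight of the point but leaves the zero rule unsuited to this endpoint.

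**Conclusion.** The point holds in conditional form. On the face of the document, NQ concentrations are set to zero for an endpoint that is itself an undosed hormone level. Pre-dose falls under a log summary that cannot accept a zero and whose NQ rule is not visible. The combination of the three samples when some are NQ is also left open.

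It would go too far to conclude that the Group 2 summaries do reflect the assay floor, or that a contraceptive effect is hidden, because Group 2 states neither its LLQ nor an NQ rate. They may largely reflect the limit if true levels are near or below it. Under the stated assumptions the bias in the mean is large at or below the LLQ, small at twice the LLQ (3-5%) and negligible at four times (0-1%). Since the plan cannot know in advance which case applies, its rule should work in all of them. For an exploratory objective, this is a change that should be made; it does not threaten the main results.

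**What to change.** In Group 2 RAP 8.3.2, with matching edits to 10.5.2 and the display list:

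1. Exempt Pre-dose from the zero rule and from the default log summary.
2. State the Group 2 LLQ, and reconcile the 2 pg/mL in Group 1 section 3.1 with the 10 pg/mL implied by the Group 1 mock shell.
3. Report, by cohort and session, the number and percentage of pre-dose samples that are NQ and of women whose pre-dose samples are NQ, in the manner of Group 1 Table 2.8.
4. Give the median and range, printing any value below the limit as `<LLQ`.
5. Say how the three pre-dose samples are combined, without averaging zeros.
6. Give a geometric mean only from a method that treats NQ values as left-censored, and only when enough samples are quantifiable, by a criterion set beforehand.

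The cost is SAP wording and one extra table from samples already scheduled. A left-censored estimate adds a distributional assumption. If NQ is frequent, the objective may end as a comparison of quantifiability between cohorts and not as an estimate of concentration.

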8.3.4.1. Statistical Methodology Specification

Endpoint / Variables

 For IH: - Cp10, Cp20, Cp30, AUC(0-3h), Cmax, Area under the concentration time curve from time zero to infinity (AUC[0-∞]) will be compared as data permit. 
Note: These endpoints will be log transformed for analysis.

Model Specification

 Mixed Effect model will be used to analyze the data. Endpoint: log transformed PK parameter Fixed effect: Cohort (COC/Non-COC) Random effect: Subject The Kenward and Roger method for approximating the denominator degrees of freedom and correcting for bias in the estimated variance-covariance of the fixed effects will be used. An unstructured covariance structure for the G matrix will be used. In the event that this model fails to converge, alternative covariance structures may be considered such as VC or CS. Akaike's Information Criteria (AIC) will be used to assist with the selection of covariance structure.

CONFIDENTIAL

205920

Model Checking & Diagnostics

 • For the Mixed Model, model assumptions will be checked, and appropriate adjustments may be applied based on the data. • Distributional assumptions underlying the model used for analysis will be examined by obtaining a normal probability plot of the residuals and a plot of the residuals versus the fitted values (i.e. checking the normality assumption and constant variance assumption of the model respectively) to gain confidence that the model assumptions are reasonable. • If there are any departures from the distributional assumptions, alternative transformations, such as data squared or square root of data, will be explored. • Non-parametric analyses will be conducted if the normality assumption does not hold.
Model Results Presentation

 • Point estimates and corresponding two-sided 90% confidence intervals for the comparison of interest that is Cohort A (COC) vs Cohort B (non-COC) for IH Oxytocin. These will then be back-transformed to provide point estimates and corresponding 90% confidence intervals for the geometric mean ratios (COC/Non-COC)
Endpoint / Variables

 • $t_{1/2}$, T_{max} Note: This endpoint will not be log transformed for analysis
Model Specification

 • Mann-Whitney test • The test will be performed for IH oxytocin only
Model Results Presentation

 • Point estimate and 90% confidence interval for the median difference COC-non COC

CONFIDENTIAL

205920

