2.3. Study Design

Overview of Study Design and Key Features	

Group 1 – Women in TSL
 <pre> graph LR A[Screening (Pregnant Subjects)] --> B[Randomisation to treatment assignment] B --> C[Oxytocin Administration as Active Management of TSL (IM or IH) - Single dose] C --> D[Follow-up 1 (within 24 hours)] D --> E[Follow-up 2 (7-14 days)] </pre> 
Group 2 – Non-pregnant, non-lactating females of child bearing potential
 <pre> graph LR A[Screening (non-pregnant volunteers)] --> B[Randomisation to treatment assignment] B --> C[Oxytocin Administration (IH or IV) - Session 1] C --> D[Minimum 48 hours maximum 14 days] D --> E[Oxytocin Administration (IH or IV) - Session 2] E --> F[Follow-up (7-21 days)] </pre>	
Design Features	
 • Group 1: This is an open-label, randomized, single dose study enrolling women in the third stage of labour who will receive either IH or IM oxytocin • Group 2: This is an open-label, randomized, two dosing, cross over study enrolling healthy, non-pregnant, non-lactating female subjects of childbearing potential who will receive IH oxytocin at one dosing session and IV oxytocin at the other dosing session. It will be divided into two cohorts: Cohort A will enrol women on a combined oral contraceptive. Cohort B will enrol women who are not using a hormonal form of contraceptive.
Dosing	
 • Group 1: Subjects will receive 400 mcg IH oxytocin or 10 I.U. IM oxytocin in one dosing session. Follow Up 1 within approximately 24 hours post dose. Follow Up 2 at least 7 days and no greater than 14 days after study drug administration. • Total duration: Screening after 18th week of pregnancy (i.e. within 168 days of 1 dosing session) + follow up of 7 - 14 days = approximately 183 days • Group 2: Subjects will receive 400 mcg IH oxytocin and 5 I.U. IV oxytocin in two dosing sessions. Follow Up will take place at least 7 days and no greater than 21 days after last study drug administration. • Total duration: Screening within 28 days of dosing session 1 + 2 dosing sessions with a maximum of 14 days between dosing + follow-up of 7 – 21 days = 64 days
Time & Events	
 • [Refer to Appendix 2: Schedule of Activities]

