10.6.2. Study Population

Demographics
Age

 • GSK standard IDSL algorithms will be used for calculating age. • Randomization date will be used as reference date to calculate age
Body Mass Index (BMI)

 • Calculated as Weight (kg) / [Height (m)]²
Extent of Exposure

 • Number of days of exposure to study drug will be calculated based on the formula: Duration of Exposure in Days = Treatment Stop Date – (Treatment Start Date) + 1 • Participants who were randomized but did not report a treatment start date will be categorised as having zero days of exposure. • The cumulative dose will be based on the formula: Cumulative Dose = Sum of (Number of Days x Total Daily Dose) • If there are any treatment breaks during the study, exposure data will be adjusted accordingly.

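### The exploratory COC versus non-COC comparison of inhaled PK contrasts non-randomised cohorts with cohort as the sole fixed effect, so a weight difference between cohorts would enter the ratio unadjusted

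*SAP*

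**What the plan says.** **How the cohorts arise.** Group 2 RAP section 2.3 states: "Cohort A will enrol women on a combined oral contraceptive. Cohort B will enrol women who are not using a hormonal form of contraceptive". Both definitions rest on the woman's existing contraception. The same section describes Group 2 as follows: "This is an open-label, randomized, two dosing, cross over study enrolling healthy, non-pregnant, non-lactating female subjects of childbearing potential". Each woman has one inhaled and one IV session, so what is randomised is their order.

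**The model.** Section 8.3.4 specifies a "mixed effect model with a fixed effect term for cohort and a random effect term for subject" for the log-transformed parameters. Section 8.3.4.1 repeats it as two lines, "Fixed effect: Cohort (COC/Non-COC" and "Random effect: Subject". It applies to Cp10, Cp20, Cp30, Cmax, AUC(0-3h) and AUC(0-∞). The Mann-Whitney analysis of t1/2 and Tmax is also unadjusted.

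**Status.** The comparison is listed among the exploratory objectives, and section 2.4 says that no formal hypothesis is tested. The result is a geometric mean ratio with a two-sided 90% interval, meant to show the plausible range.

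**Other comparisons.** IV by cohort is descriptive only (Group 2 RAP 2.4). Inhaled versus IM, and Group 1 versus Group 2, have no statistical comparison (Group 1 RAP, Table 1).

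**The concern.** The cohorts are two self-formed groups of women and may differ in body size. If exposure depends on weight, part of the COC/non-COC ratio is a weight difference. The model cannot separate the two. The random subject term does not help: with one inhaled record per woman it is indistinguishable from residual error, and the analysis amounts to an unadjusted two-sample comparison on the log scale.

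Recruiting more women would narrow the interval without moving its centre. The RAP nowhere says that the cohorts are not randomised. Its labels are those of a treatment comparison: section 2.4 speaks of test and reference treatments, section 5.1 lists the contrast under treatment comparisons, and shell PK_T1 has Test and Ref columns. A reader of the study report could take the ratio for more than an observational contrast.

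**Working it through.** The RAP states no sample size, SD or expected effect for this comparison, so there is no planned figure to reproduce. The steps below use its model with assumed inputs.

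**1. Weight.** Model: log(parameter) = mean + cohort + error, one inhaled record per woman, true ratio 1. If AUC varies as weight to the power -b, then

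expected ratio = (mean weight in COC / mean weight in non-COC)^(-b).

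The exponent range (b = 0.5 to 1) and the weight gaps are assumptions.

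| COC cohort weight | b = 0.5 | b = 1 |
|---|---|---|
| 5% heavier | 1.05^-0.5 = 0.976 | 1.05^-1 = 0.952 |
| 10% heavier | 1.10^-0.5 = 0.953 | 1.10^-1 = 0.909 |
| 15% heavier | 1.15^-0.5 = 0.933 | 1.15^-1 = 0.870 |
| 10% lighter | 0.90^-0.5 = 1.054 | 0.90^-1 = 1.111 |

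No sample size enters the formula, so the shift does not shrink with recruitment.

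**2. Shift against interval width.** Assume a log-SD of 0.5 and 10 women per cohort. The standard error is 0.5 × √(2/10) = 0.224 and t(0.95, 18) is 1.734, so the 90% interval around a ratio of 1 is exp(±0.388), or 0.68 to 1.47. In simulation with these values, b = 0.75 and a 10% heavier COC cohort (10,000 runs per setting), the average ratio was 0.93. Coverage of the 90% interval was 0.88 without a session effect and 0.88 to 0.91 across all settings. The centre is displaced, but at this size the interval is wide enough that coverage hardly changes.

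**3. Session order.** Let θ be the session 2/session 1 ratio and pA, pB the shares of each cohort inhaling in session 2. Then the ratio is θ^(pA - pB). Randomising order makes pA - pB zero on average. With no weight gap and θ of 1.25 or 1.5, simulation gave average ratios of 0.996 to 1.000 and coverage of 0.90 to 0.92, whether order was balanced or simply randomised. Only chance imbalance matters in a single trial: θ = 1.25 and pA - pB = 0.2 give 1.25^0.2 = 1.046.

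**4. Cost of adjusting for weight.** Degrees of freedom: weight plus sequence takes 2n - 2 to 2n - 4, and the 90% t multiplier rises by a factor of 1.012 at n = 8 and 1.003 at n = 15 per cohort (assumed sizes). Collinearity: with a mean log-weight difference d and a within-cohort log-weight SD s, the standard error of the cohort effect grows by about √(1 + d²/(4s²)). Assume s = 0.15:

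- 10% gap: d = ln 1.10 = 0.0953; √(1 + 0.00908/0.09) = 1.05
- 15% gap: d = ln 1.15 = 0.1398; √(1 + 0.0195/0.09) = 1.10

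This is before any reduction in residual variance, and it is slightly larger in very small cohorts.

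**The case against.** The strongest reply is that an unadjusted ratio is a legitimate summary of how two populations differ, and the objective asks only for a comparison between cohorts. The analysis is exploratory, tests no hypothesis and runs only if data suffice. Nothing in the document shows that the cohorts differ in weight; eligibility limits may sit in the protocol, which is not at hand. The exponent is argued for AUC and need not carry over to Cmax or the timed concentrations. Under the assumptions above, a shift of 5 to 9% lies well inside the interval. All of this stands. It limits the point to a supporting analysis and a statement of what the ratio is.

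Three safeguards might be cited. Table 1.4 summarises demographics by cohort, which can reveal an imbalance but does not correct the ratio. Bioavailability F, summarised by cohort, divides each woman's inhaled exposure by her own IV exposure, so weight effects common to both routes largely cancel; that is useful context, but it is a different quantity and has no cohort model. The provision in 8.3.4.1 for adjustments based on the data belongs to the checks of model assumptions and names no covariate; residual plots would not reveal confounding by weight.

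Two stronger readings are tempting. One is that session order also biases the ratio. It does not, because order is randomised; omitting it leaves chance imbalance and extra residual variance, which the interval accommodates. The RAP does not say whether randomisation was stratified by cohort. The other is that the plan presents the ratio as a causal contraceptive effect in a formal test. The labels invite that inference, but no sentence states it, and section 2.4 disclaims formal hypotheses.

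**Conclusion.** The point holds as a cheap improvement. In the plan's only inferential comparison, the cohorts are not randomised and cohort is the only fixed effect, so any weight difference enters the geometric mean ratio and is not reflected in its 90% interval. For AUC, a 10% weight gap would move the ratio to about 0.95 to 0.91 if COC users are heavier, or 1.05 to 1.11 if lighter, with no true effect. Those figures rest wholly on an assumed exponent and an assumed gap; the document supports neither a direction nor a size for this trial. Session order is not part of the bias.

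**What to change.** - In Group 2 RAP section 8.3.4.1, prespecify a supporting model for the six log-transformed parameters: log parameter = cohort + log body weight, optionally + sequence (inhaled first or second). The weight slope is estimated for each parameter, so no exponent need be assumed. A sequence term would only remove chance imbalance and residual variance.
- In Table 2.4, report the adjusted COC/non-COC ratio and 90% interval beside the cohort-only ratio, which stays as planned.
- In section 2.4, state that the cohorts are not randomised and that the ratio is an observational contrast.

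No new data should be needed: section 10.6.2 derives BMI from weight, and Figure 2.7 is already paged by treatment sequence. The cost is RAP wording, one or two degrees of freedom, and a standard error about 5 to 10% larger if the weight gap is 10 to 15% (assumed log-weight SD 0.15), before any gain from lower residual variance. Keeping the unadjusted ratio in the table means that this loss of precision falls only on the supporting result.
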